The StepRite system developed by MedHab (<http://www.medhab.com/>) allows the physical therapist to monitor physical activity and exercise remotely, thereby reducing the need for frequent out-patient visits. A thin insole placed inside the shoe measures foot contact pressure and acceleration. This information is translated into quantitative feedback about exercise compliance and performance measures comparing the surgical side with the non-surgical side. Real time feedback during exercise and weight-bearing activities is

provided to the patient, and a HIPAA secured user interface website also displays this information in an online dashboard for both physical therapists and the physician.

With the advent of federally mandated bundled payments for total joint replacement, active management of the rehabilitative process postoperatively with quantifiable data will be necessary to ensure financial stability.

Given the potential for improving patient engagement with rehabilitation, this study proposes a treatment model which includes monitoring activity outside of the clinic using the StepRite device and using a combination of outpatient appointments and remote consultations with therapists.

Significance of this study

The significance of the proposed study includes the projected benefit to the patients in terms of attaining clinical outcomes quicker and to the medical system in terms of managing cost for the provision of services. Subjects are expected to demonstrate improved compliance to patient tailored rehabilitation protocols which will lead to more rapid attainment of clinical outcomes versus present traditional rehabilitation methodologies. The expected level of, and rate of, attainment of clinical outcomes will translate to an overall reduction of cost to the medical system by reducing the need to engage in additional processes or the need to protract the time required to attain clinical outcomes, where either or both in combination can increase rehabilitation expenditures.

Objectives

To compare the efficacy of StepRite in a prescribed physical therapy program verses traditional in-facility physical therapy program after partial or primary total knee replacement using validated survey tools to evaluate patient progress, including patient self-reporting of progress and surgeon appraisal of patient performance post-operatively.

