through the use of Steprite. Importantly, care for patients is delivered as part of current adopted standards utilizing outcome measurements, the use of which and the interpretation of which is already built into care provided by the clinical facility, thereby negating the need to develop additional outcome measures. Recruitment of 30 patients will come from the investigators' normal patient population, among patients who are scheduled for partial or total knee arthroplasty. As there is no change in post op care for these patients from the investigators standard protocols other than monitoring and enforcement of home protocols, the same therapists involved in investigators' normal patient care will be involved with both arms of the study.

For this study, 30 patients represents a sample size deemed acceptable as a starting point. There are no other published studies using Steprite in comparative design trials. Determinations of sample size needed for this study, using 80% power and significance of 0.05, incorporate the use of a time frame in days or weeks for completion of the rehabilitation protocols that would allow for the detection of clinically significant differences between the group using Steprite and those using conventional therapies only. Given that conventional therapies can include skilled nursing, home health and outpatient visits and given that the need for each of these is highly variable dependent on the patient, it is difficult to assign a time value for determinations of sample size.

With that, a sample size of 30 participants divided into two groups represents an initial starting point, with the potential of incremental addition of more patients in order to achieve significance between the two study groups.

Statistical significance will be evaluated utilizing a standard t-test for two group comparison.

In preparation for the study, MedHab Inc. will at their expense train all involved investigators and therapists in the fitting and use of the StepRite device. Medhab will also train a lead therapist designated by the lead investigator to be in charge of overseeing and monitoring, ensuring proper use of the device. There is no cost to the patient, hospital or other funding entity for participation in this study. Medhab LLC will assume all costs associated with the training, application, device and use of the StepRite product for the full course of this study.

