Subjects for this study will be recruited from the patient population seen by the investigators during the normal course of business. There will be no outside recruitment of individuals or advertising as to the presence or use of the monitoring device to entice new patient referral. Prospective candidates will be asked by the lead investigator at the time they are designated surgical candidates. All documentation related to the study will be reviewed with the patient by the lead physician or his designee who is appropriately trained in discussing patient recruitment. Final decision and randomization to control or StepRite use will be done as part of the preoperative checkup just prior to surgery where both operative consent and study consent are discussed and signed.

Randomization:

Once a patient agrees to the study they would be sequentially randomized into whether or not they receive StepRite. The patients will be randomized to every other eligible patient gets the intervention. (ie: 1,3,5,7,9... will get StepRite ; 2,4,6,8 will not get StepRite) 15 Intervention subjects will be recruited and 15 control subjects will be recruited with an extra 5 patients to account for attrition and withdrawals.

Schedule of events

The intervention group will receive the StepRite device with standard conventional care and the control group will receive standard conventional care only. Both groups will receive outpatient, home health, and /or 24 hour physical therapy treatment plans per their surgeon's standard of care. The control group will undergo the conventional outpatient treatment program to 8 weeks as normally prescribed by the lead investigator. This consists of a twice weekly outpatient appointment with a physical therapist and prescribed home exercise program (see attached physical therapy protocol).

The patients randomly selected to wear the StepRite inserts will be fitted and instructed along with the patient's designated care giver in their use including initial pre-op measurements prior to their surgical date so that data collection can begin on the 1st day of rehab after surgery

Those patients not selected to wear step rite will receive instructions preoperatively of their expected therapy regimen and receive their baseline functional evaluation of the knee

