Both groups will be given log sheets to record their activity at home and when seen by the physical therapist. These will be returned and collected by the therapist weekly and scanned into/ kept in the patient's medical record file. A paper copy will be kept in the coordinator's office, 4A144B with the consent forms and any other study documents.

Both groups will also have routine self-assessment questionnaires (appendices 3, 4 KOOS and KSS) and functional testing performed by the PI and PT during the patient's regular clinic visit as standard of care.

Outcome measurements performed just after surgery and at time of discharge from hospital and standard of care post-surgical clinic visits to 8 weeks will indicate if any patients are experiencing unexpected delays in progress. Subjects will be visited at home by the Home Health therapists, and will visit and receive telephone consultations with the outpatient therapists, who will be able to monitor the patients' conditions and intervene if there are any problems related to the use of the device. The StepRite device will provide the therapist with more information about the patients' activity levels and progress than would usually be available to them and so is not expected to have any safety implications. The device and App. will prompt the patient with voice and text to complete their exercises as they are needed, while collecting data.

Device Flow Chart: standard of care post-op

The research coordinator will consent the patient prior to the surgery

The research coordinator will document the following information for the device on the device data collection form. (See attached)

- a. Name of patient
- b. Email of patient
- c. Phone number of patient
- d. Surgery date
- e. Expected date of discharge

The patient's information will then be entered into the steprite™ system and a patient account will be created by the Research Coordinator

Physical therapy will schedule the study protocol via the steprite™ system and enter the physical therapy start date as day after discharge.

MedHab™ sponsor ([name]) will contact the patient for the patient account set up and to obtain the following signatures required by MedHab (see attached)

- a. HIPAA
- b. Assignment of Benefits

MedHab™ will help the patient load the app, provide an overview of the app, and forward a tutorial video
MedHab™ will send the steprite™ device to the study Research Coordinator at TTUHSC

TTUHSC Orthopaedic Surgery

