There is a risk of loss of confidentiality, we will have measures in place to help prevent any loss of personal information. During the course of this study there are no new or additional steps required of the subjects from what is considered the standard protocol for the lead investigator. The only alteration may be reduced travel and outpatient visit by the patient if compliance and functional improvement noted by the therapist. StepRite imparts no energy to the patient and poses no hazard to patient well being. Subjects will be free to withdraw from the study at any time and revert to conventional rehabilitation treatment.

Possible benefits to subjects

There is a possibility the device group patient could benefit from the device prompting them to do their own exercises regularly, which could lead to a faster recovery and better physical therapy outcomes. We are hoping the participation in this study may help us learn how we can design rehabilitation programs to be more effective in the future.

Confidentiality measures

StepRite / MedHab will have access to non-PHI patient data collected by the device stored on their HIPPA compliant server and be available only to the lead investigator. All PHI will be kept separate from the study data in a locked filing cabinet or on a password protected computer in the research coordinators office in 4A144B.

Data Collection and Monitoring

Data recorded by the StepRite device will be transmitted wirelessly to the HIPAA secured web interface managed by Medhab. Clinicians will be able to log into the website with a password to review the progress of each patient.

Data recorded by the PI and physical therapist on the functional motion of the knee will be recorded in paper form and kept with the completed KOOS questionnaire and Knee Society Score (KSS) and scanned into the patients HIPPA protected chart.

Upon completion of patient's part in the study MedHab will contact UMC and the Therapy departments to acquire actual costs of these services. This will be done to compare the overall cost of management of the post-operative rehabilitation of a patient in traditional rehabilitative regimen vs. use of StepRite,

Actual Cost information for the patient's full rehabilitation will be requested and collected by the Hospital and released to MedHab at the end of the study and supplied to the lead investigator for analysis.

References

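### The protocol body plans no record of harms or returns to care, in either arm, to set beside the cost result

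*Combined protocol and SAP*

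**What the plan says.** On safety, the Risks section says that "StepRite imparts no energy to the patient and poses no hazard to patient well being". The only risk it names is loss of confidentiality. Schedule of events adds that the device is not expected to affect safety.

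On the care model, Background says the system lets the therapist "monitor physical activity and exercise remotely, thereby reducing the need for frequent out-patient visits" and describes treatment "using a combination of outpatient appointments and remote consultations with therapists". Risks says: "The only alteration may be reduced travel and outpatient visit by the patient if compliance and functional improvement noted by the therapist". Study Design and Methods, however, says post-operative care is unchanged "other than monitoring and enforcement of home protocols". Schedule of events gives the device arm StepRite on top of conventional care, and Control Subject flow gives controls the same standard care without the device. The conventional outpatient programme runs to 8 weeks: "This consists of a twice weekly outpatient appointment with a physical therapist and prescribed home exercise program".

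On monitoring, Schedule of events says outcome measures will reveal unexpected delays in recovery, and that therapists can watch patients' conditions and "intervene if there are any problems related to the use of the device". The principal investigator (PI) sees patients at weeks 2, 6 and 12.

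On records, "Both groups will be given log sheets to record their activity at home and when seen by the physical therapist", and therapists collect these sheets weekly. The other data named are knee motion, the KOOS, KSS and LEFS surveys, device data and cost. Data Collection and Monitoring describes the cost data as the cost of rehabilitation, requested from the hospital and the therapy departments. The second null hypothesis is about cost to the medical system.

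**The concern.** The no-hazard sentence concerns the insole, and nothing here disputes that the insole is low risk. What the trial tests is the insole together with a possible shift from in-person to remote contact. Less cost because of fewer visits is a good result only if patients do not come back in other ways: a fall, a wound problem seen elsewhere, an unplanned visit, a readmission, a further procedure on the knee. The protocol body asks nobody to count these.

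The loss is partly permanent. Readmissions and procedures at the study hospital can be recovered later from its records. Falls, minor wound or skin problems and care given elsewhere are harder to recover, because a record exists only if someone asked and wrote it down. If the plan is followed as written, a cost difference could be reported with no returns to care beside it, and the safety statement would rest on no data.

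**Working it through.** **Step 1. What is recorded.** No figure in the plan bears on this point, so the check is a reading of each data source named in the protocol body.

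| Source | Where | Arms | Event record? |
|---|---|---|---|
| Activity logs, collected weekly | Schedule of events | Both | Activity only, as described |
| KOOS, KSS, LEFS | Device Flow Chart; Schedule of events | Both | Symptoms and function, no events listed |
| Knee motion and functional testing | Data Collection and Monitoring; Schedule of events | Both | No |
| Outcome measures to week 8 | Schedule of events | Both | Flags slow progress; no event definition or count |
| Therapist watch for device problems | Schedule of events | Device users only, by nature | No recording specified |
| PI visits, weeks 2, 6, 12 | Device Flow Chart | Both, as standard care | No event items specified |
| Device data | Data Collection and Monitoring | Device | No |
| Cost | Data Collection and Monitoring | Both | Cost of rehabilitation, not events |

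Falls, wound problems, unplanned visits, readmissions and further procedures appear in none of these.

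**Step 2. Whether the cost data fill the gap.** The request goes to the hospital and the therapy departments, so some returns to care might appear. But the data are described as rehabilitation cost, and a readmission need not be classed as that. Care at other institutions would not appear. The hypothesis is wider than the data described.

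**Step 3. Size of the contact difference.** The protocol gives no number for the reduction in visits, and makes it conditional. Three sections say standard care is otherwise the same. The reduction could be zero, and no percentage gap in contact can be derived.

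**Step 4. What a common record could show.** Inputs: 15 patients per arm (Study Design and Methods); the event counts are illustrative.

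- Zero events in 15, one-sided 95% upper bound: 1 − 0.05^(1/15) = 0.181, or about 18%.
- Zero events in both arms, Newcombe 95% interval for the difference in risk. The Wilson upper limit for 0/15 is z²/(n + z²) = 3.84/(15 + 3.84) = 0.204, so the interval is −20 to +20 percentage points.
- One event against none. The Wilson limits for 1/15 are 0.012 and 0.298. Lower: 0.067 − √[(0.067 − 0.012)² + 0.204²] = −0.144. Upper: 0.067 + (0.298 − 0.067) = 0.298. The interval is −14 to +30 points.
- Chance of seeing at least one event in an arm of 15 if the true risk were 5% (assumed): 1 − 0.95^15 = 0.54. At an assumed 2% it is 1 − 0.98^15 = 0.26.

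The table would be descriptive. Even an event-free trial would be compatible with a risk of up to about 18% in an arm.

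**The case against.** The strongest reply is that these patients are well watched. Outcome measures are scheduled to find delayed recovery, therapists see or telephone patients, home health therapists visit, therapy can be extended, and the PI sees patients three times. Telephone consultations are described for subjects generally, not only for device users. Any cut in visits applies only when the therapist judges the patient to be doing well. All of this stands as clinical care. It does not supply a defined list of events, a time window or a count by arm.

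A second reply is that event fields would normally sit on the log sheet or on the therapy and clinic forms, which are not in the text available. That also stands, and it limits the point to the protocol body.

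A third is that 30 patients cannot establish safety. That is agreed, and it is why no test is proposed. It also cuts against a flat statement that there is no hazard.

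Three stronger readings are tempting and should be resisted:

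- A reader might infer that device patients will be seen in person much less often than controls. The documents do not support this: the reduction is conditional and unsized, standard care is said to be the same in both arms, and home health visits, which are also in person, are not counted anywhere.
- A reader might infer that StepRite or remote care is unsafe, or that harms will be under-counted in the device arm. Nothing in the documents shows either. Device patients may be seen less in person but are monitored more remotely, so the direction of any bias is unknown.
- A reader might infer that the cost comparison is invalid. The gap affects how a saving can be interpreted; it does not by itself invalidate the comparison.

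**Conclusion.** The point holds for the protocol body. No common record of harms or returns to care is planned in either arm, while the protocol states that there is no hazard, allows for fewer outpatient visits with the device, and seeks a conclusion on cost to the medical system from data described as rehabilitation cost. This should be changed as a cheap improvement to what is collected and reported.

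Two conditions apply. The unseen forms must not already contain such items. The precision figures assume 15 analysed patients per arm. Confidence is moderate because of the first condition.

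**What to change.** Unless an attached form already does this:

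- Add a short yes/no list to the weekly log sheets that both groups return, for as long as the logs run: fall, wound or skin problem, unplanned visit, readmission, further knee procedure.
- Ask the same items at the existing PI visits at weeks 2, 6 and 12, covering the time since the last log.
- Send any yes to the PI. Confirm readmissions and procedures from hospital records.
- Tabulate counts by arm through week 12, descriptively and without a test, beside the cost result.
- Reword the safety sentence to say that no hazard is expected and that events are recorded in both arms.

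The rule for reducing visits and the management of events stay with the investigators.

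The cost is a few lines on an existing form, a record check for 30 patients (35 if all those requested enrol), one table and an amendment. No visits are added. The downside is slightly more recording by patients and by usual-care therapists, whose departments are not study specific and who would need a short briefing. Some differential reporting will remain because no blinding is described, and the report should say so. After the logs stop, events up to week 12 depend on recall at the remaining PI visits.

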The patient or designated care giver will be responsible for placing the insoles on their charging platform nightly.

Indicate the number of patients/charts/surveys/specimens needed.

The total number of patients needed in this study is 30, we will request a total of 35 to account for possible Attrition or withdrawals. 15 will be fitted with the StepRite device and 15 will follow the normal postoperative protocol without the device and be considered control subjects.

Inclusion criteria

Unilateral Partial or Total knee arthroplasty.

Age 45-75 yr. old

BMI <35

Access to Wi-Fi

Have appropriate smart phone and knowledge of use

Be willing to place StepRite app on their personal phone

Exclusion criteria

History of neuromuscular disorder (e.g. Parkinson's, Polio, or stroke).

Pregnancy

History of cognitive disease that would preclude ability to navigate smart phone

Method of identifying and recruiting subjects.

Recruitment will come from the investigators normal patient population who are scheduled for a partial or total knee replacement. The Investigators will identify and consult the research coordinator to assess eligibility.

Compensation given to subjects.

There will be no compensation given to subjects. They will be allowed to keep the insoles and access the app for at home therapy at no cost to them for as long as the device works.

Describe the site(s) where study will be done.

The main clinical/surgical portion of the study will take place at Texas Tech University Health Sciences Center department of Orthopaedic Surgery and University Medical Center Lubbock. The physical therapy departments used for this study will be the investigators preferences and standard of care, therefore they would be used if not on the study and are not study specific.

MedHab LLC (StepRite) will be collecting data from several sites to compare outcomes and cost. The secondary sites utilizing this device and doing similar studies are Covenant with [name] as the lead investigator, the Lubbock Heart Hospital with [name] as the lead investigator, and Texas Health Resources with [name] as lead investigator. All the secondary sites will use their standard of care preferences for clinical/surgical and physical therapy. TTUHSC will not be collecting data nor in any way be affiliated with the secondary study sites. They will acquire their local IRB approval for each site separately using similar device protocols.

Risks

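### Nothing in the plan ensures that remote therapist time enters the StepRite cost comparison, and unadjusted department prices could hide a saving

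*Combined protocol and SAP*

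**What the plan says.** Cost to the medical system is one of the two objectives and the subject of the second null hypothesis (Objectives; Hypothesis and specific aims). The costing method is in Data Collection and Monitoring. After a patient finishes, "MedHab will contact UMC and the Therapy departments to acquire actual costs of these services", and "Actual Cost information for the patient's full rehabilitation will be requested and collected by the Hospital and released to MedHab", after which it goes to the lead investigator for analysis. No section lists the services to be counted, defines actual cost, sets a unit price or says how remote therapist time is valued.

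The services and their providers vary. Study Design and Methods says that "conventional therapies can include skilled nursing, home health and outpatient visits". The section describing the sites says "The physical therapy departments used for this study will be the investigators preferences and standard of care".

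On the treatment model, Background describes monitoring outside the clinic "using a combination of outpatient appointments and remote consultations with therapists", with an online dashboard for therapists and physician. Schedule of events says subjects "will visit and receive telephone consultations with the outpatient therapists". Risks says: "The only alteration may be reduced travel and outpatient visit by the patient", conditional on compliance and functional improvement. The conventional outpatient programme in Schedule of events is a "twice weekly outpatient appointment with a physical therapist", continued to 8 weeks.

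The only analysis named is a standard two-group t-test with 15 patients per arm (Study Design and Methods).

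**The concern.** Two separate matters arise, and the first is the better grounded in the documents.

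**Remote time.** If StepRite works as intended, some in-person contact gives way to telephone contact and dashboard review. That work uses therapist time, and it reaches the comparison only if a department happens to cost it as a service. If it is not costed, the error has a known direction: the arm that substitutes remote for in-person contact looks cheaper than it is. The time cannot be recovered reliably afterwards, because costs are requested only once a patient has completed the study.

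**Department prices.** A patient's actual cost is the quantity of services multiplied by the price at the department attended. StepRite can change only the quantity. Departments are not assigned or stratified by the study, and the t-test does not account for them. If their prices differ, that spread enters the error term of an already small comparison and can hide a real saving.

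**Working it through.** **Figures in the plan.** There is no cost figure to reproduce. The sample size of 30 stands beside 80% power and 0.05 significance, but no difference or SD is given. Working backwards for 15 per arm, two-sided, the detectable standardised difference is (1.960 + 0.842) × √(2/15) = 1.02, or 1.06 with the exact t distribution. The cost comparison therefore has little precision to spare.

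**Remote time.** From the documents: twice weekly × 8 weeks = 16 outpatient visits. Assumed: 4 visits saved (4/16 = 25%), 45 minutes per visit, and remote work twice weekly for 8 weeks (16 contacts).

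- Time saved: 4 × 45 = 180 minutes.
- Remote time at 5, 10 or 15 minutes per contact: 16 × 5 = 80, 16 × 10 = 160, 16 × 15 = 240 minutes.
- Offset: 80/180 = 44%, 160/180 = 89%, 240/180 = 133%.

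A second form avoids assuming minutes. Suppose 4 visits are replaced by 4 calls, each costing a fraction f of a visit. The true saving is 4 × (1 − f)/16, while 25% is reported if calls carry no cost.

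| f | True saving | Reported if calls uncosted |
|---|---|---|
| 0 | 25% | 25% |
| 0.25 | 18.75% | 25% |
| 0.50 | 12.5% | 25% |
| 1 | 0% | 25% |

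**Department prices.** Assumed: three equally used departments with relative prices 1 and 1 ± 1.2247 × CV; use of department unrelated to arm; normally distributed visits with mean 16 in control and 12 with StepRite; 15 per arm; t-test on visits × price; 20,000 simulated trials per cell.

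| Visit SD (% of 16) | One price | Price CV 15% | Price CV 30% |
|---|---|---|---|
| 20% | 91% | 78% | about 49% |
| 30% | 59% | 52% | 36% |

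In every cell the mean arm difference stays at about 4.0 visit-equivalents. With no true effect the rejection rate stays near 5%. Price spread unrelated to arm therefore costs power and does not move the expected difference.

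A different set-up shows the same pattern. With two equally used departments and a visit SD of 4, power is about 75% at one price and 71%, 57% and 38% at price ratios of 1.2, 1.5 and 2.0.

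**Chance imbalance in a single trial.** With two equally used departments, the probability that the arms differ by 3 or more patients in the dearer one is 36%. At a price ratio of 1.5, a split of 9 v 6 moves the difference by 16 × (0.5/1.25) × (3/15) = 1.28 visit-equivalents, which is 1.28/16 = 8.0%, with no change in services used. The t-test's error rate allows for this, but the point estimate carries it.

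**The case against.** A reader might infer that differences in department price will be mistaken for a StepRite effect. The documents do not support that. They give no prices, do not say that prices differ, and do not say that department use differs by arm. The departments are those the patients would use outside the study, and Study Design and Methods says the same therapists serve both arms, which makes an uneven split less likely. Systematic bias needs department to differ by arm. Allocation by strict alternation is predictable and not stratified by department, so it does not rule this out, but nothing shows that it happens. The larger price spreads above are also generous: a CV of 30% makes the dearest of three departments 1.367/0.633 = 2.16 times the cheapest.

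A reader might also infer that remote time is left out. That is not shown either. The request is for cost of the patient's full rehabilitation, which could include it. The sentence on telephone consultations refers to subjects, in a passage about both groups, so calls may occur in both arms and part of the error would then cancel. Therapist communication follows an attached therapy protocol that is not available here and may specify the amount of contact. The offsets also treat therapist minutes as the whole cost of a visit.

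Finally, actual cost is a defensible main measure, because the hypothesis concerns cost to the medical system. Price noise can be handled without replacing it: in the three-department model with a visit SD of 20%, regressing log cost on arm and department gives about 88% power at either price CV, against 78% and about 49% unadjusted.

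These points stand. They remove the claim of price-driven bias and the case for demoting actual cost. What remains is the absence of any rule for recording or costing remote time, and the absence of any allowance for department.

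**Conclusion.** The point holds in a limited form. The plan does not ensure that therapist time spent on remote contact and dashboard review is recorded or costed, although that time may replace visits. If departments do not cost it, the StepRite saving is overstated. The amount is unknown: the 44%, 89% and 133% offsets are illustrations that rest on the assumed number of visits saved, visit length, contact length and contact frequency.

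Department price differences, if they exist and are unrelated to arm, add noise and can hide a saving. The fall in power from 91% to 78% or about 49% depends on three departments, a visit SD of 20%, a 25% cut and the stated price CVs, none of which comes from the documents. With a visit SD of 30%, power is only 59% even at one price, so in that case small numbers are the larger problem.

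This should be corrected before enrolment, because the missing counts have to be collected as care is given. It is a gap in the costing method, not an arithmetic error.

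**What to change.** For every patient in both arms, record prospectively:

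- the therapy department attended;
- counts of outpatient visits, home-health visits and facility days;
- minutes of telephone contact and of dashboard review, as two fields on a therapist contact sheet. The existing patient log sheets are not tied to the cost comparison, and nothing says that they capture this time.

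State what actual cost includes. Keep it as a main measure, with remote minutes valued and added, and account for department in its analysis through a model specified in advance. If that model uses log cost, give the arithmetic mean difference as well, since the hypothesis concerns total cost. Beside it, report a cost that applies one unit-price list to the counted services in both arms, so that a difference in quantity can be told apart from a difference in price.

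The cost is two extra fields for therapists, one price list and a slightly longer analysis. Patient care does not change.
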